The main analysis will be based on intention-to-treat principles. To test the effect of the intervention on the short term outcomes at 6 months, we will use a residualized change score to determine whether the intervention and control groups differ in change in outcome (e.g., weight and HbA1c) from baseline, controlling for baseline values. The analysis uses regression with the dependent variable being the change in weight (or HbA1c) at 6 months and the independent variables are baseline weight (or HbA1c) and a dummy variable for study arm (intervention versus control). To examine the long-term effect of the intervention we will use multilevel modeling to examine the trajectory of the outcomes across baseline, 6, 12, and 18 months. Weight (or HbA1c) is the dependent variable; time, study arm, and the time by study arm interaction are the independent variables. Quadratic models will be fit to the data, as it is anticipated that the change over time will not be linear throughout the 18 month period. These approaches will also be used for the analysis of the short-term and long-term effects of the intervention on other outcomes: waist circumference, fasting glucose, serum lipid profile, dietary intake (total energy, simple carbohydrates, saturated fat, number of servings of fruits and vegetables, dietary fiber and whole grains), and PA.

Assessment of success in sustainability phase

To evaluate the success of the implementation of the intervention into clinical practice at VGMHC, the average percentage of behavioral strategies, participant objectives, session content completed across sessions, average number of participants recruited, average participant satisfaction, percent of sessions attended in each phase, and average weight change will be reported. These numbers will be compared to the benchmark numbers established during the clinical trial phase of the study.

Additional Analyses

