We will also examine health literacy and numeracy and acculturation as potential moderators of the impact of the intervention by including interaction terms in the residualized change and multilevel models. Acculturation and health literacy and numeracy will be added to the models as main effects along with the interaction of these variables and the study arm. A significant interaction would signify that the effect of the intervention varies by the level of the moderator. Since these analyses may not be sufficiently powered, effect sizes as well as statistical significance will be of interest. We will also explore the effect of the intervention on quality of life over the 18 month period using the multilevel approach outlined above.

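### The long-term moderator model has no moderator-by-time term, so its moderator-by-arm coefficient does not estimate moderation of the effect on change

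*Combined protocol and SAP*

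**What the plan says.** Statistical Analysis defines two models. The 6-month model regresses change on baseline value and arm. The long-term model is "multilevel modeling to examine the trajectory of the outcomes across baseline, 6, 12, and 18 months". Its dependent variable is the outcome itself, and "time, study arm, and the time by study arm interaction are the independent variables". It adds that "Quadratic models will be fit to the data". The same two models serve waist circumference, glucose, lipids, diet and physical activity: "These approaches will also be used for the analysis of the short-term and long-term effects of the intervention on other outcomes".

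Additional Analyses examines health literacy and numeracy and acculturation as moderators "by including interaction terms in the residualized change and multilevel models". It then specifies the terms: the moderators "will be added to the models as main effects along with the interaction of these variables and the study arm". No moderator term with time is named anywhere. On interpretation it says "A significant interaction would signify that the effect of the intervention varies by the level of the moderator", and, because power may be low, "effect sizes as well as statistical significance will be of interest".

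**The concern.** One recipe is applied to two models with different dependent variables. Where the outcome is change, moderator-by-arm is the moderation of the intervention effect. Where the outcome is the level at four visits with baseline among them, the intervention effect is carried by time-by-arm, so its moderation is carried by moderator-by-arm-by-time. Without that term the long-term model can only shift the arms by a constant within each moderator level.

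What is at stake is the effect size. The plan falls back on it because significance may be out of reach, and in the long-term model it is the quantity that would be misread.

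**Working it through.** **Structure (no assumed figures).** With arm A (0/1) and moderator M (0/1), the model as written is

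E[Y(t)] = b0 + b1·t + b2·t² + A·(g0 + g1·t + g2·t²) + d·M + h·M·A.

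The arm difference at time t is g0 + g1·t + g2·t² + h·M. Between M = 1 and M = 0 it differs by h at every visit, including t = 0. The moderation of change from baseline is therefore h − h = 0, whatever the data. The generalized least-squares (GLS) estimate of h is a weighted average of the moderator-by-arm contrast over all four visits, baseline included.

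**Inputs for the size.** The documents give N = 200 (Eligibility), equal allocation (Baseline Data Collection and Randomization) and visits at 0, 6, 12 and 18 months. They give no SD, correlation or moderation size, so there is no planned figure to reproduce. *Assumed:* a binary 50/50 moderator (50 women per cell), no dropout, weight with between-woman SD 12, 15 or 18 kg, residual SD 2.5 kg, independent random slopes with SD 0 or 0.25 kg/month, two-sided 5% tests, and a true moderation of 0 at baseline and 2 kg at every follow-up.

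**Terms as written, slope SD 0.** The visit weights are 0.25 each.
- Expected h = 0.75 × 2 = 1.5 kg.
- SE = √[(4/50)(SD² + 2.5²/4)]. For SD 12 this is √[0.08 × (144 + 1.5625)] = 3.41 kg; for SD 15, 4.26; for SD 18, 5.10.
- Power = Φ(h/SE − 1.96) + Φ(−h/SE − 1.96). With 1.5/3.41 = 0.44 this is 0.072; for SD 15 and 18 it is 0.064 and 0.060.
- P(wrong sign) = Φ(−h/SE) = 0.330, 0.362 and 0.384.

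**Terms as written, slope SD 0.25.** The weights are proportional to 1 − 0.0596·t, that is 0.54, 0.35, 0.15 and −0.04.
- Expected h = (1 − 0.54) × 2 = 0.92 kg.
- SE is 3.43, 4.27 and 5.12; power 0.058, 0.055 and 0.054; wrong sign 0.394, 0.415 and 0.429.

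**Three-way terms (linear and quadratic) added.** The between-woman SD cancels out of contrasts from baseline. A quadratic cannot follow a step exactly. For slope SD 0, the least-squares quadratic through 0, 2, 2, 2 is 0.1, 1.7, 2.3, 1.9, giving changes of 1.6, 2.2 and 1.8 kg; the contrasts are the same for slope SD 0.25.

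| Slope SD | SE at 6/12/18 months (kg) | Wrong sign at 6/12/18 months | Joint 2-df power |
|---|---|---|---|
| 0 | 0.77/0.95/0.95 | 0.019/0.010/0.029 | 0.553 |
| 0.25 | 0.88/1.27/1.59 | 0.035/0.042/0.128 | 0.349 |

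For slope SD 0, the fitted values have mean 1.5 and squared deviations 1.96 + 0.04 + 0.64 + 0.16 = 2.80. The noncentrality is 2.80/(4 × 6.25/50) = 5.6, which gives the power of 0.553.

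**Other cases.** With 4 kg of moderation, power is 6–14% as written against 91–99% for the joint test. With no moderation at all, the coefficient as written exceeds 2 kg in absolute value in 56–70% of trials; the three-way contrasts do so in 1–21%.

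**Noisier outcomes.** Assume residual SD 1, a random intercept only, and a step of 0.5.

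| Within-person correlation | Power as written | Joint three-way | Joint three-way, baseline constrained |
|---|---|---|---|
| 0.90 | 7% | 24% | 26% |
| 0.80 | 10% | 24% | 28% |
| 0.50 | 22% | 24% | 38% |
| 0.33 | 34% | 24% | 47% |
| 0.20 | 47% | 24% | 56% |

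The test as written and the unconstrained joint test break even at a correlation of about 0.46. In every row the coefficient as written still has expectation 0.75 × 0.5 = 0.375 rather than 0.5.

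**The case against.** The strongest reply is that one sentence covers two models and may be shorthand: crossing the moderator with study arm could mean crossing it with whatever term carries the effect, which in the long-term model is time-by-arm. A three-way term may well have been intended. But the plural in the general statement is explained by there being several moderators, and the sentence that lists the terms stops at moderator-by-arm. An analyst who follows the text would not fit the three-way term.

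Several other points stand and limit the concern.

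- The moderators are collected at baseline (Recruitment), so randomization makes the expected baseline moderator-by-arm difference zero. Type I error is intact, and a significant result is valid, if weak, evidence that the effect varies. The plan's sentence on significance is not itself wrong; the reading of the effect size is.
- The kilogram figures depend on assumed SDs. A between-woman SD of 12–18 kg with a residual SD of 2.5 kg implies a within-person correlation of about 0.96–0.98 without random slopes, close to the worst case for a level contrast.
- For outcomes with a correlation below about 0.46, the unconstrained three-way test has less power than the test as written. The documents do not show which outcomes those are.
- The analysis is exploratory, the plan already warns of low power, and at 2 kg the repaired test reaches only 35–55%.

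None of this makes the coefficient an estimate of moderation of change.

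**Conclusion.** The concern holds for the long-term multilevel model as written. The moderator-by-arm coefficient is a time-constant level difference that includes baseline, and the model imposes equal arm differences in change at every moderator level. That follows from the listed terms alone.

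Under the weight assumptions above, a true 2 kg moderation appears as 1.5 or 0.92 kg with a standard error of 3.4–5.1 kg, so even its sign is unreliable. The power advantage of the three-way test is specific to highly correlated outcomes, whereas the wrong target is common to all outcomes.

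The 6-month moderator model, type I error, and the primary and secondary conclusions are not affected. The plan should be corrected, but the trial's main results do not depend on it.

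**What to change.** In Additional Analyses, state that the long-term moderator models add moderator-by-time and moderator-by-arm-by-time terms, linear and quadratic to match the main model. Test the three-way terms jointly, and report moderator-specific arm differences in change from baseline at 6, 12 and 18 months. Keep moderator-by-arm alone for the 6-month residualized change model only.

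For noisy outcomes, consider constraining the baseline arm and moderator-by-arm differences to zero, which randomization justifies for moderators measured at baseline. In the cases tabulated this gave more power than the test as written at every correlation.

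The cost is one sentence, no new data, and four more parameters per binary or continuous moderator. Without the baseline constraint, some power is lost for outcomes with a within-person correlation below about 0.46. Power stays limited if moderation is small, as the plan already acknowledges.

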Participants assigned to the usual care control condition will receive printed materials (in English and/or Spanish) developed by the NHLBI on how to improve weight-related behaviors ("Steps to Lose Weight," "ChooseMyPlate," "Nutrition and Finding Your Way to a Healthier You"). We recognize that literacy limitations will reduce the usefulness of these materials for some of our participants, but providing this type of printed materials is our approximation of the best "usual care" practices currently available at VGMHC. Participants in both the intervention and the enhanced usual care control arms will receive a bathroom scale, a set of measuring cups and spoons, and a pedometer (with printed instructions and tips for increasing physical activity).

Follow-up data for all randomized participants will be collected at 6, 12 and 18 months following randomization. Physical data collection (height, weight, waist circumference, blood draws) will be completed at the VGMHC clinic; all other data collection will be done by telephone interview. All data-collection staff will be female and bilingual, and masked to participant treatment assignment.

Explanatory Session and Consent Visit

Explanatory sessions will be conducted by a bilingual study staff member who will provide a thorough overview of the study, including the intervention, design, and requirements for weekly group meetings, planned data collection, and duration of follow up. Attendees will be encouraged to ask questions. Then, the study consent will be discussed, and women interested in enrolling in the study will meet individually with study staff to address additional questions, confirm eligibility, and sign the consent form. Those who consent will be measured for height and weight, and will be scheduled for baseline bilingual assessment interviews conducted by telephone in the next 2 weeks. The telephone baseline assessment will include a food frequency questionnaire and physical activity questionnaire.

Participants may take their consent home to return at a later time but must return to the VGMHC with their consent form, to be witnessed and signed, and have their baseline measurements taken.

We have revised the consent to include sharing of participants PHI with Arizona State University. PhD candidate students in the Department of Nutrition will conduct the follow up SW FFQ interviews and, if needed due to literacy issues, conduct the Follow Up visit questionnaire by phone.

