The weight loss program is designed to achieve weight loss through dietary calorie reduction, increased energy expenditure through physical activity, and improved self-efficacy through behavioral self-management.

Dietary recommendations:

1. Consume ~500 fewer calories per day to achieve ½-2 lb weight loss per week.
2. Eat a healthy dietary pattern (i.e., the DASH eating style and WLM program, a diet rich in fruits, vegetables, and low-fat dairy foods, and low in fat).
3. Limit alcohol consumption to no more than one drink per day.

Physical activity recommendations:

4. In addition to normal daily activities, exercise at moderate intensity most days per week.
5. Progress gradually to 30-60 minutes/day to a weekly target of at least 180 minutes.

Behavioral recommendations:

6. Record daily food intake and physical activity.
7. Set short-term goals and create action plans.
8. Be an active study participant by attending intervention group sessions.

Measures

Weight will be measured with participants in light indoor clothes without shoes, and determined to the nearest 0.1 kg by a calibrated digital scale.

Height will be measured at enrollment to the nearest 0.1 cm using a calibrated, wall-mounted stadiometer.

Waist circumference will be measured at the midpoint between the lower rib and the iliac crest. We will record this to the nearest 0.5 cm. Measurement will be done with a Linen non-stretch tape measure with a tension device to provide a constant tension during measurement.

HbA1c and fasting lipids, and glucose will be collected in the course of patient care, using point-of-care devices to facilitate data collection by VGMHC staff members. Data will be collected for all trial participants at baseline, 6-, 12-, and 18-months post randomization. For participants that are unable to come to the clinic for the blood draw, we will do a home outreach and collect the sample at their homes.

Fasting lipids (total cholesterol, HDL-cholesterol, and triglycerides) will be measured enzymatically (Lipid Panel Plus Reagent Disc; Henry Schein, Inc, Melville, NY) in whole blood using a Piccolo Blood Chemistry Analyzer (Abaxis Inc., Union City, CA). LDL-cholesterol will be calculated using the Friedewald equation.⁹⁶ Fasting

glucose will be measured using a OneTouch Ultra blood glucose monitoring system (LifeScan, Inc. Milpitas, CA). HbA1c will be measured from capillary blood using an A1cNow+ device (Bayer HealthCare LLC,

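### The moderator analysis reads a significant interaction as a varying effect across about 30 to 90 possible tests, with no stated alpha or multiplicity control

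*Combined protocol and SAP*

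**What the plan says.** The Additional Analyses section states: "We will also examine health literacy and numeracy and acculturation as potential moderators of the impact of the intervention". It does this by "including interaction terms in the residualized change and multilevel models", so both the 6-month model and the 18-month model are in play. The rule for reading the result is "A significant interaction would signify that the effect of the intervention varies by the level of the moderator". The next sentence adds: "Since these analyses may not be sufficiently powered, effect sizes as well as statistical significance will be of interest".

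The section does not say which outcomes receive moderator tests. The Statistical Analysis section applies the two models first to test "whether the intervention and control groups differ in change in outcome (e.g., weight and HbA1c) from baseline", and then to "other outcomes: waist circumference, fasting glucose, serum lipid profile, dietary intake (total energy, simple carbohydrates, saturated fat, number of servings of fruits and vegetables", followed by fibre, whole grains and physical activity. No significance level and no multiplicity adjustment appears anywhere in the document.

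On the control arm, the Recruitment section says of the printed handouts: "We recognize that literacy limitations will reduce the usefulness of these materials for some of our participants". The section on weight management tools puts this more softly, as a possible problem for some participants. The Enhanced Usual Care Control section presents the information-only comparator as a deliberate choice.

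**The concern.** The rule turns a p-value into a finding. Applied to every combination of outcome, moderator and model that the text allows, it will often produce a significant interaction when no moderation exists. The accompanying caution is about power. It warns that a real moderator may be missed, and does nothing about one that is not real. Low power in fact makes the problem worse, because fewer of the significant results are then true ones.

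A reported moderator would be a natural reason to steer the programme towards or away from women with limited literacy or lower acculturation. The document does not say that the results will be used in this way, but it plans a sustainability phase in the same clinic.

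A second, smaller issue is how a literacy interaction is described. The plan itself expects the control handouts to be less useful to some women with limited literacy. The arm difference could therefore vary with literacy because the control response varies. The plan does not provide for results by moderator level within each arm, so a reader could not see where an interaction comes from.

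**Working it through.** The documents give no figure to reproduce: no alpha, number of tests or error rate is stated.

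**Step 1. Count the tests.**

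| Input | Source | Value |
|---|---|---|
| Weight, HbA1c | Statistical Analysis | 2 |
| Waist, fasting glucose | Statistical Analysis | 2 |
| Lipids | Measures: "Fasting lipids (total cholesterol, HDL-cholesterol, and triglycerides) will be measured enzymatically", plus calculated LDL | 4 |
| Diet: energy, simple carbohydrates, saturated fat, fruit and vegetables, fibre, whole grains | Statistical Analysis | 6 |
| Physical activity | Statistical Analysis | 1 |
| **Outcomes** | | **15** |
| Moderators | Additional Analyses; 2 if literacy and numeracy form one score, 3 if separate | 2–3 |
| Models | Additional Analyses names two; 1 is the lower bound, if only one is used per outcome | 1–2 |

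Lowest count: 15 × 2 × 1 = 30. Highest count: 15 × 3 × 2 = 90. Splitting fruit from vegetables would give 16 × 3 × 2 = 96. Quality of life is not counted. The section names only a moderator-by-arm term. If interactions with time were also tested in the multilevel model, the count would rise further.

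**Step 2. Error rates under a global null, independent tests.** Alpha is an assumption: 0.05 unadjusted, with 0.01 for range. Expected false positives = alpha × k. Chance of at least one = 1 − (1 − alpha)^k.

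| k | Expected at 0.05 | At least one, 0.05 | At least one, 0.01 |
|---|---|---|---|
| 30 | 1.5 | 0.785 | 0.260 |
| 45 | 2.25 | 0.901 | 0.364 |
| 60 | 3.0 | 0.954 | 0.453 |
| 90 | 4.5 | 0.990 | 0.595 |

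**Step 3. Allow for correlation.** Correlation leaves the expected number unchanged but lowers the chance of at least one. Test statistics were simulated as multivariate normal with assumed correlations, at the 5% level.

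| Tests | Between outcomes | Between moderators | Between models | At least one |
|---|---|---|---|---|
| 90 | 0–0.6 | 0–0.6 | 0–0.8 | 0.76–0.99 |
| 90 | 0.2–0.4 | 0–0.6 | 0–0.8 | 0.87–0.98 |
| 60 | 0.2–0.6 | 0.3 | 0.8 | 0.68–0.88 |

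Taking the last two rows together gives roughly 0.7 to 0.98. The 30-test case was not simulated; with positively correlated tests it would lie below 0.785.

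**Step 4. Would a smaller set be enough without adjustment?** Weight and waist in one model give 2 × 2 = 4 to 2 × 3 = 6 tests, with a chance of at least one false positive of 0.19 to 0.26 if independent. Both models with three moderators give 12 tests: 0.46 if independent, 0.31 to 0.34 in the correlated simulation. A short list helps but still needs adjustment. Bonferroni over all 90 would require 0.05/90 = 0.00056 per test.

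**Step 5. An interaction that comes from the control arm.** Assume that the intervention arm loses 4 kg at both literacy levels, and that the control arm loses 1 kg at high and 0 kg at low literacy. The interaction is (4 − 0) − (4 − 1) = 1 kg, although the intervention arm changed equally at both levels.

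For a median split with equal arms, the variance of the interaction is 16 × SD²/N. With N = 200 and an assumed SD of 5 kg the standard error is √2 = 1.41 kg, so power at 1 kg is about 0.105. Over assumed SDs of 5–7 kg and N of 160–200, power is 7–11% at 1 kg, 15–29% at 2 kg and 27–56% at 3 kg.

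**The case against.** The strongest reply is that the plan already signals caution. The analyses sit under an additional heading, the variables are called potential moderators, and effect sizes are to be considered alongside significance. The text does not say that every outcome will be tested, and it fixes no alpha, so the 90-test figure is an upper reading. This is fair, and it rules out saying that the plan treats significance as proof. It does not remove the problem. The framing never says hypothesis-generating, the sentence that interprets significance stands, and nothing narrows the outcomes.

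On the control arm, the reply is largely right. In a randomised trial the intervention effect is the contrast with control, and this information-only control was chosen on purpose. A reader might infer that an interaction arising from the control arm is a false or misattributed result. The documents do not support that: it is real modification of this contrast, and is misread only if reported as the programme itself working differently. The documents give it no size, and a 1 kg difference would seldom reach significance. The printed materials are bilingual, both arms also receive tools that do not depend on print, and the intervention itself asks women to keep daily records, so literacy could act through either arm. The literacy argument does not directly cover acculturation.

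A reader might also want to accept a moderator only if the intervention arm's own slope shows it. That would be unsound. Literacy is not randomised, so a within-arm slope mixes prognosis with effect.

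**Conclusion.** The concern holds for multiplicity and interpretation. If the sentence is followed across the outcomes the models cover, at an unadjusted 5% level, at least one false moderator is likely: 0.79 to 0.99 under independence for 30 to 90 tests, and roughly 0.7 to 0.98 for 60 to 90 tests under plausible correlation, with 1.5 to 4.5 false positives expected. These figures rest on an assumed alpha, assumed correlations, a global null and a count that the plan does not state. At 0.01 the independent figures fall to 0.26 to 0.60.

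A reader might conclude that a false moderator is close to certain. That needs 90 tests, independence and alpha 0.05 together, and the documents establish none of the three. The control-arm issue supports an extra descriptive display and careful wording, not a claim of error.

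**What to change.** Replace the sentence that interprets a significant interaction. The new text should say that:

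- the moderator analyses are hypothesis-generating;
- the outcomes, moderators and models tested, and hence the number of tests, will be stated;
- interactions will be reported as estimates with confidence intervals;
- no claim of moderation will be made from an unadjusted p-value.

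If the sponsor wants to be able to claim moderation, name a small set in advance on the Aim 1 outcomes (weight and waist), state alpha, and adjust over that set, for example by Holm. Which time points to include is the sponsor's choice, since Aim 1 covers 6, 12 and 18 months.

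Beside each interaction, show change by moderator level within each arm. This is descriptive and not a pass/fail rule. Describe any literacy interaction as a difference in the contrast with this control.

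The cost is a few sentences and one table from models already planned, with no new data. The downside is that fewer moderator results can be called significant.
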